- Multiple seizure types or Faciobrachial dystonic seizures
- AED Resistance
- Personal or family history (1st degree relative) of autoimmunity
- History of recent or past Neoplasia
- Evidence of CNS inflammation on CSF (elevated protein, pleocytosis, oligoclonal bands, + CSF index)
- Evidence of CNS inflammation on MRI (mesial temporal or other regional T2 hyperintensity)
- Hypometabolism/hypermotabolism on functional/PET imaging
- Detection of neural autoantibody

IVIg in autoimmune epilepsy: Autoimmune epilepsy is increasingly recognized in the spectrum of neurological disorders characterized by detection of neural autoantibodies in serum or spinal fluid and responsiveness to immunotherapy. We recently performed a retrospective review of 29 patients treated with 6-12 weeks of intravenous methylprednisolone or immune globulin, or both (the current standard immunotherapy trial protocol used at Mayo Clinic), for suspected autoimmune epilepsy.⁹ Similar to AED trials, treated patients were considered “responders” if there was a 50% or greater reduction in seizure frequency. A total of 18 patients (62%) responded favorably to the immunotherapy trial (Figure 2). Ten of these (56%) achieved seizure freedom and the remainder had more than 50% reduction in seizure frequency. Five of eleven responders with daily seizures (45%) became seizure free after completion of the immunotherapy trial, 45% had only monthly seizures and 1/11 (9%) had weekly seizures. Two out of 4 responders with weekly seizures (50%) became seizure free and the other two had monthly seizures. All three responders with monthly seizures became seizure free. None of the responders who had generalized tonic-clonic seizures at presentation (8/18; 44%) continued having these after completion of the trial. Fifteen patients (52%) responded to the first agent tried and 14 (48%) did not. Having failed the first agent, 3 of 7 patients (43%) responded to a second agent (Figure 2). Of the fifteen patients who improved with the first immunotherapy trial, 6 responded within the first week, 6 responded in the second to fourth weeks and one required treatment for 5 weeks before improvement was noted.

Figure 2. Flow-chart of "immunotherapy trial" and response according to antibody type.

[figure not shown]

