Overall we found that all 12 patients with VGKC complex antibodies responded. Two of six patients with GAD65 antibodies and 5 of 10 patients either with plasma membrane antibodies not known to be associated with encephalitis or who lacked any neural antibody were responders (Figure 2). Of 23 patients who underwent IVMP therapy as 1st line therapy, 10 were considered non-responders: IVIG therapy was administered to 5 of these non-responders and 40% had $\geq 50\%$ reduction in their seizure frequency. Of 6 receiving IVIG as 1st line therapy 33% had $\geq 50\%$ reduction in their seizure frequency. These retrospective findings justify consideration of a diagnostic trial of immunotherapy in patients with autoimmune epilepsy (with or without neural autoantibodies). Since all patients with VGKC complex antibodies receiving immunotherapy were responders, these patients will serve as the basis for this first randomized controlled trial.

In our original systematic analysis of 32 patients with suspected autoimmune epilepsy, we reported that 63% had memory and cognitive difficulties and 25% had personality change. Given this high frequency of cognitive problems, and our prior data indicating significant benefits in cognitive performance post immunotherapy in patients with autoimmune encephalopathies with or without seizures, we suggest that neuropsychological assessments be performed at baseline and after treatment. We have previously shown that autoimmune cognitive disorders also are highly responsive to immunotherapy.

In 2010, our group also treated 72 consecutive patients with suspected autoimmune cognitive disorders (all with cognitive dysfunction [amnesia, executive dysfunction, behavioral change]) as the predominant presenting symptom.¹⁵ Seizures were also encountered in 25% of the patients. Forty-six patients (64%) improved (documented in 80% by the Kokmen Short Test of Mental Status [Figure 3], neuropsychological testing [Figure 4], or both). Pretreatment and posttreatment neuropsychological score comparisons revealed improvement in almost all cognitive domains, most notably learning and memory. Immunotherapy responsiveness was predicted by a subacute onset ($p < .001$), fluctuating

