- This will be a post-trial observational follow up of all patients. The treating clinician will randomly assign patients to receive no treatment or immunotherapy.
- The immunotherapy will be mycophenolate mofetil with IVIG taper. This may be changed to alternative immunotherapies if the patient's insurance denies coverage.

3 Study Design

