Patients will keep a daily seizure diary. Patients will be seen at 6 months and 12 months as part of standard clinical care (neurological examination will be recorded). A study coordinator will call patients every month after completion of the study infusions to review seizure history, medications, and adverse events. Relapse will be defined as $\geq 20\%$ increase in seizure frequency (# seizures per week) compared with the post IVIG weekly seizure frequency. Cognition will be assessed by the study coordinator who will perform Telephone Interview for Cognitive Status (TICS) and the KOKMEN at each monthly call.²¹

If a relapse occurs, the patient will be seen at the clinic as standard of care. Patients on no therapy will be started on immunotherapy per current standard of care. Those on therapy will have treatment adjusted as per current standard of clinical care.

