7.2 Endpoints

Primary endpoints*

- 1) Change in seizure frequency

The definition of a “responder” is a patient with a $\geq 50\%$ reduction in seizure frequency.

Secondary endpoints

Clinical factors predictive of immunotherapy response.

The following clinical factors will be analyzed with respect to prediction/correlation with favorable outcome.

- 1) Interval from symptom onset to immunotherapy treatment
- 2) Type of onset
- 2) Clinical course
- 3) Seizure type and frequency
- 4) EEG abnormalities
- 5) Presence of other neurological symptoms or signs (tremor, headache, myoclonus)
- 6) CSF findings (White cell count; protein)
- 7) Neural autoantibody type (LGI1, CASPR2, other) and titer (blood draws will be performed at baseline, 6 weeks and 12 weeks (for placebo group only)
- 8) Change in The Repeatable Battery for the Assessment of Neuropsychological Status (RBANS) scale scores

Tertiary endpoints

For the 1 year follow up “observational study”

- “Responder” patients from Trial will be randomly assigned to 2 clinical groups:
 - Immunotherapy (as per physician/insurance approval): mycophenolate mofetil 2000mg daily or azathioprine 2mg/kg +/- IVIG taper or IVMP taper
 - No immunotherapy
- Subjects will be followed for relapse for a total of 12 months (see study schedule of events).
- Patients will keep a daily seizure diary and record any adverse events while on immunotherapy.
- The study coordinator will call patients every month review seizure history and adverse events.
- Patients will be seen at 6 months and 12 months as part of standard clinical care-neurological examination will be recorded.
- Relapse will be defined as $\geq 20\%$ increase in seizure frequency compared with post IVIG frequency.
- Cognition will be assessed by the study coordinator who will perform Telephone Interview for Cognitive Status and the KOKMEN at each monthly call.
- If relapse occurs, the patient will be seen at the clinic. Patients on no therapy will be started on immunotherapy, those on therapy will have treatment adjusted as per current standard clinical care.

8 Safety and Adverse Events

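### Tertiary aim: the clinician's random assignment has no stated method, and the 20% relapse rule has no zero-reference convention and, if applied at each monthly call, would often flag stable patients

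*Combined protocol and SAP*

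**What the plan says.** Section 2 (Tertiary Aim) states: "The treating clinician will randomly assign patients to receive no treatment or immunotherapy". Section 3.2 narrows this to responders and says that the treating physician makes the assignment open label. Section 7.2 also limits it to responders. None of these sections gives a ratio, a sequence or a means of concealment. Section 5.3 has the research pharmacy randomise 1:1, but only between drug and placebo.

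Section 3.2 defines relapse as a rise of at least 20%: "increase in seizure frequency (# seizures per week) compared with the post IVIG weekly seizure frequency". Section 7.2 repeats the threshold as an "increase in seizure frequency compared with post IVIG frequency". Neither gives a rule for a zero reference, a period over which either rate is measured, or a confirmation step. Section 3.2 also attaches treatment to the label: "Patients on no therapy will be started on immunotherapy per current standard of care", and patients already on therapy have it adjusted.

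The aim is tertiary and is called observational. No test, power or error rate is stated for relapse.

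**The concern.** There are two separate weaknesses.

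**Assignment.** If the clinician who knows the patient chooses the group, and nothing fixes the choice in advance, patients expected to relapse can be steered towards treatment. Calling the result random would then claim more than the procedure supports.

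**Endpoint.** A percentage rise cannot be computed from zero, and seizure freedom is a likely outcome in responders. In responders with a few residual seizures, a 20% rise over a short period can be less than one seizure, so ordinary variation will often cross the line. Because the same label starts or changes immunotherapy, a chance flag would not only misclassify a patient. It would also move someone in the untreated group onto treatment and blur the comparison that the aim is meant to make.

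**Working it through.** **The plan's own figure.** There is none for relapse. The only power figure concerns the primary endpoint (section 7.1: 70% versus 10%, 15 per group, 89%). Exact enumeration of the two-sided Fisher test gives 89.4%, so it reproduces, and nothing below touches it.

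**Seizure-free share (section 1.1).** Responders with daily seizures: 5 of 11 became seizure free. Responders with weekly seizures: "Two out of 4 responders with weekly seizures (50%) became seizure free and the other two had monthly seizures". Together (5 + 2)/(11 + 4) = 7/15 = 47%, exact 95% CI 21-73%. The other eight had monthly (5 + 2 = 7) or weekly (1) seizures. The pilot mixed antibody types and mostly used methylprednisolone first ("Of 23 patients who underwent IVMP therapy as 1st line therapy", out of 29), so this is a guide and not an estimate for this trial.

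**Zero reference.** The relative rise is (F - R)/R, with R the reference and F the later rate. At R = 0 it is 0/0 or x/0. Rewritten as F >= 1.2 x R, it would count a patient who stays at zero (0 >= 0). The convention has to be stated. Zero counts also arise in patients who still have seizures: at 0.25 per week, a four-week window is empty with probability exp(-1) = 37%.

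**Count noise in stable patients.** Assumptions, none of which the documents give: independent Poisson counts, a four-week reference and four-week looks. R and each F_j are Poisson with mean 4 x rate, and the true rate never changes. A call is flagged if F_j >= 1.2 x R; patients with R = 0 are left out. By hand, for 1 per week and a reference known to be 4: 1.2 x 4 = 4.8, so five seizures suffice, and P(Poisson(4) >= 5) = 37%. With the reference itself estimated (simulation, 200,000 patients per rate):

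| Seizures per week | One given call | At least once in 12 calls | At two consecutive calls in 12 |
|---|---|---|---|
| 0.25 | 18% | 77% | 30% |
| 0.5 | 32% | 86% | 54% |
| 1 | 41% | 84% | 62% |
| 2 | 37% | 81% | 54% |
| 7 | 25% | 69% | 38% |
| 14 | 17% | 56% | 26% |
| 28 | 9% | 37% | 13% |

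For 0.25 to 14 per week the ranges are 56-86% unconfirmed and 26-62% confirmed. With eleven calls they are 55-85% and 25-61%. Overdispersion does not rescue the rule: with variance twice the mean and a known reference, one call is flagged 36% of the time at 1 per week and 22% at 7 per week.

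**Number of calls.** Section 6.10 lists weeks 16 to 56 for everyone (11 calls) and week 60 for the placebo group (12). Section 6.15 adds week 10 for the IVIG group (12 and 12), which leaves six weeks to the next call. Section 3.1 says monthly.

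**Size of the comparison.** If 70% of all 30 respond, 0.70 x 30 = 21, or 10 to 11 per group. For 5 relapses in 10 the exact 95% CI is 19-81%.

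**The case against.** *The zero case has an ordinary reading.* Staying at zero is no increase, and going from zero to any seizure is one. That is fair. A reader might infer that about half of responders cannot be classified at all, and the documents do not support that: what is missing is a convention that one sentence can supply. It still has to be written down, because the plan does not say whether a single seizure in a year counts as relapse.

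*The pilot share may not carry over.* A reader might prefer the larger figure in section 1.1 ("Ten of these (56%) achieved seizure freedom and the remainder had more than 50% reduction in seizure frequency", that is, of 18). It includes three responders with monthly seizures, who fall below this trial's entry rate of two per week, so 7/15 is the closer match. Even there, the four weekly-seizure patients may have been below two per week, and seizure freedom among the antibody-positive patients alone is not given.

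*No monthly test is stated.* This also stands. The plan has a daily diary, calls and a clinic visit on relapse; it does not say that each four-week count is judged alone. It would be wrong to read the noise figures as what will happen. But the plan offers no other scheme, and a milder one does not remove the problem: one comparison of the whole follow-up period with a four-week reference still flags 11-39% of stable patients at 0.25 to 14 per week. At higher residual rates the noise shrinks, as the last row of the table shows.

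*Insurance refusals.* A reader might infer that they break the assignment. Section 2 lets a refusal change the agent, not the group, so this is not part of the point.

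*A new analysis endpoint will often be seen only after treatment has changed.* While the 20% rule remains the clinical trigger, this is true. It is why the two uses of the label must be reconciled.

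**Conclusion.** The point holds for the tertiary aim only, as something to consider. The firmest part is the assignment: a random allocation is claimed, no method is described, and a group able to supply one already works on the trial. The relapse rule lacks a zero-reference convention and measurement windows. If it is applied at each four-weekly call, it would flag a majority of stable patients with residual seizures at 0.25 to 14 per week at least once in a year, and confirming the same 20% rise at the next call leaves 26-62%. Those figures rest on Poisson counts, four-week windows and independent looks. The rates above one per week are also assumed; the pilot's residual rates were monthly or weekly. The comparison is small and no test is planned for it. The primary endpoint, its test and its power are not affected.

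**What to change.** 1. **Assignment.** Have the research pharmacy issue a concealed 1:1 list for responders, and analyse by assigned group. Otherwise delete the word randomly and report a non-randomised comparison. Cost: one more list.

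2. **Analysis endpoint only.** Fix the reference window and the look window, state what counts after a zero reference, and replace the single-look 20% rule with a confirmed criterion that the sponsor sets by simulation to lie above count noise. No threshold is proposed here. The reference window needs care: the four weeks before the week 6 or week 12 visit overlap the infusions, and in the pilot "6 responded in the second to fourth weeks and one required treatment for 5 weeks before improvement was noted"; a window after that visit would begin after assignment if patients are assigned there. Cost: wording in sections 3.2 and 7.2 and a short simulation; the diary and calls already exist. Downside: relapse is confirmed about one call later, and small rises may be missed.

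3. **Link to treatment.** The sponsor should reconcile the clinical trigger in section 3.2 with the analysis endpoint, state how treatment started or changed before confirmation is counted, and report such changes by group. The clinical trigger itself is the sponsor's decision.

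4. **Minor wording.** Reconcile section 2, which assigns patients, with sections 3.2 and 7.2, which assign responders, and align the call schedules in sections 3.1, 6.10 and 6.15.

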3.3 Primary Study Endpoints

Reduction of 50% or more, in seizure frequency with IVIG treatment.

3.4 Secondary Study Endpoints

Improvement of 20% or more in cognitive function measured by Repeatable Battery for the Assessment of Neuropsychological Status (RBANS)

3.5 Primary Safety Endpoints

- IVIG is a well-known drug and is used routinely in medical practice. We will however as a part of the primary endpoints evaluate the safety and tolerability of IVIG in VGKC Ab associated autoimmune epilepsy.

4 Subject Selection Enrollment and Withdrawal

Target accrual: 30 participants

4.1 Inclusion Criteria

- Seropositivity for VGKC complex antibodies (value $>0.1\text{nM}$; normal $\leq 0.02\text{nM}$) or positive for LGI1/CASPR2 Ab by CBA.
- And ≥ 2 seizures per week (mean of total over 1 week)
- Male or female between the ages of 18 and 85 years of age
- Women and men of child bearing potential must agree to use a reliable form of contraception throughout the course of the study.
- Homecare treatment agency available at place of residence, or agreeable to travel to Mayo Clinic in the rare event of unavailability of the homecare agency. (This information will be known by the patient and study team before consenting to the study).
- On a stable dose of antiepileptic medications (unable to change while receiving IVIG/placebo) or on no treatment

4.2 Exclusion Criteria

- History of thrombotic episodes within the 2 years prior to enrolment
- History of status epilepticus within the last year
- Known allergic or other severe reactions to blood products including intolerance to previous IVIG
- Previous adequate trial of IVIG as determined by the Principal Investigator
- IgA deficiency
- Prior failed trial of high dose steroid (prednisone $>60\text{mg}$ daily or methylprednisolone $>1\text{g}$ weekly for >2 weeks)
- Reproductive status:
 - Women who are pregnant,
 - Women who are breastfeeding,
 - Women and men of childbearing potential who are unwilling or unable to use an acceptable method of birth control to avoid pregnancy for the entire study period, as evaluated by the investigator. (Women of non-childbearing potential are those that have a history of hysterectomy, bilateral oophorectomy, or are postmenopausal with no history of menstrual flow for > 12 months prior to screen visit.)
- Any surgical procedure (except for minor surgeries) within 4 weeks prior to baseline.
- Evidence of serious uncontrolled concomitant diseases that may preclude patient participation (physician determined), as described; Other nervous system disease, cardiovascular disease, hematologic/hematopoiesis disease, respiratory disease, muscular disease, endocrine disease, renal/urologic disease, digestive system disease, congenital or acquired severe immunodeficiency
- Known active infection (excluding fungal infections of nail beds or caries dentium) within 4 weeks prior to baseline.
- Evidence of chronic active hepatitis B or C.
- Active ischemic heart disease in the past year prior to baseline.
- Patients should not have severe renal or hepatic disease (determined by treating physician).
- Severe hypertension (diastolic pressure >120 mmHg or systolic >170 mmHg).

4.3 Subject Recruitment, Enrollment and Screening

Since our preliminary data indicate a high likelihood of response (80-100%) for patients with VGKC Abs we intend to randomize 30 patients to allow a powered study. Patients will be identified through Mayo Clinic's Neuroimmunology Laboratory [100,000 patients sera tested annually for neural

autoantibodies (~10,000 positive) on a clinical service basis], Autoimmune Neurology Clinic's close interactions with the Epilepsy neurology groups, and referrals through ClinicalTrials.gov website. Patients will be asked to keep a daily seizure diary (minimum of 1 week), before they come for their first evaluation at Mayo Clinic.

4.4 Early Withdrawal of Subjects

4.4.1 When and How to Withdraw Subjects

Patients are allowed to withdraw consent at any time. Every effort should be made to ensure patients are willing to comply with trial participation prior to conducting the screening procedures and the patients should be fully informed of the restrictions related to the change of concomitant medications during the trial. Investigators may choose to discontinue a patient's treatment because of AEs, as well as conditions or illnesses that preclude compliance with the protocol from the standpoint of the patient's safety or well-being. The study staff should notify the Sponsor of all trial withdrawals as soon as possible. The reason for patient discontinuation must be recorded in the source documents and CRF.

Reasons subjects may be withdrawn from this research study

- Subject safety issues
- Failure of subject to adhere to protocol requirements
- Disease progression or a 50% increase in seizure frequency (compared to baseline).
- Subject decision to withdraw from the study (withdrawal of consent)
- Severe allergic reaction that call for hospitalization.
- Any thrombotic event
- Status epilepticus

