All patients will receive phone calls from the clinical research coordinator at 2 weeks, 4 weeks to assess patient reported side effects and record seizure diary information. The placebo group that will receive IVIG in an open label fashion, will also receive phone calls every week (weeks 7-11) to assess patient reported side effects and record seizure diary information. Any side effects or increase in seizure frequency from previous baseline will be reported to the principal investigator or designee to determine if any action should be taken or if un-blinding is required. Patients will also be given 24 hour emergency contact information for the study team to carry with them at all times.

Treatment location:

First 4 infusions will be given at Mayo Clinic using Mayo's standard operating procedures for infusion administration (see appendix 1). This will allow study personnel to closely evaluate the patient and give the home care network time to set the home treatment.

Home infusions:

The 4 IVIG infusions for those 15 initial placebo group patients will be given at the patient's home or clinic near their home. These infusions will be given per Option Care's standard operating procedure (see appendix 2)

In this study we are going to utilize the home care network of Option Care nationwide. Therefore one of the inclusion criteria is that the home treatment network is available where the patient lives.

Our secondary aim firstly investigates clinical factors predictive of IVIG response. These will include antibody type (LGI1, CASPR2, other) and titer. Thus blood draws will be performed at baseline, 6 weeks and 12 weeks (for placebo only). Secondly, we will assess for improvements in cognitive performance as measured by the KOKMEN¹⁷ and the Repeatable Battery for the Assessment of Neuropsychological Status (RBANS).²⁰

Our tertiary aim, a clinical observational study, investigates factors influencing relapse rate after a positive IVIG response. "Responders" from AIM 1 will be randomly assigned in open label fashion by the treating physician to 2 clinical observational groups:

- Immunotherapy (as per physician/insurance approval): mycophenolate mofetil 2000mg daily or azathioprine 2mg/kg +/- IVIG taper or IVMP taper
- No immunotherapy

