8.5 Stopping Rules

Autoimmune epilepsy in the presence of anti VGKC antibodies has not been proved to respond better to IVIG than to no treatment at all. There has not been an open label or a phase 3 trial regarding treatment and outcome, and there are no guidelines or recommendations regarding treatment. There is only level III evidence to support treatment in these patients. Moreover, some patients spontaneously recover back to baseline. Since not easy to diagnose (because of the presenting symptoms often being non convulsive), many times treatment is started months after symptoms start and still prognosis is

good. Therefore we feel comfortable to delay treatment for 5 weeks in the placebo group. We did however decide on stopping rules to prevent any serious implications of delaying treatment.

All participants shall have contact information for the study coordinator. Any adverse event should be reported to the coordinator within 24-48 hours by the patient. The principle investigator will be informed and take the proper steps to ensure patient safety.

1. Severe allergic reaction that call for hospitalization.
2. Any thrombotic event
3. Status epilepticus
4. Increased seizure frequency (more than 50% compared to base line).

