8.6.1 Internal Data and Safety Monitoring Plan

1. Subject Safety

All subjects enrolled into this study will undergo safety assessments (vital signs, weight, safety blood tests, and cardiac status) at various time points throughout the study. Any abnormal finding will be reported to the PI immediately upon receiving the results.

Subjects will receive phone calls the week after their infusions in which study seizure diaries will be reviewed at all visits for adverse events and any addition or stoppage of new or current medications. This information will be documented in the subject’s study binder. Any information that is collected and is considered abnormal will also be reported to the PI as soon as possible.

All participants shall have contact information for the study coordinator. Any serious adverse event should be reported to the coordinator within 24-48 hours by the patient. The principle investigator will be informed and take the proper steps to ensure patient safety (reporting to the IRB per institutional guidelines and reporting to the sponsor).

1. Severe allergic reaction that call for hospitalization.
2. Any thrombotic event
3. Status epilepticus
4. Increased seizure frequency (more than 50% compared to base line)

In the event PI is not available, the Co-Investigator will be notified of any abnormal findings.

2. Data Integrity

Study inclusion and exclusion will be reviewed with each potential subject to ensure appropriateness for enrollment into the study. Study documents will be completed at the time of the visit and will be entered into the EDC (electronic data capture) system. All data queries will be adjudicated in a timely manner to ensure transcription of data is accurate and complete. The study monitor will have access to the study files and visits to the laboratory and pharmacy will be pre-arranged for the monitor. The PI/Co-I and study team will be available during the monitoring visits.

3. Subject Privacy

Subjects will be seen on Mayo-8 in a clinical exam room. All subjects will have the study explained to them in detail by a qualified member of the study team. The signing of the consent will not occur until all subjects and/or other family members have had ample time to review the consent form and have all their questions answered by the study team.

4. Data Confidentiality

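### The seizure-worsening rule has two thresholds, no counting period and differing reporting duties across sections 3.2, 4.4.1, 8.5 and 8.6.1, and needs to be reconciled

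*Combined protocol and SAP*

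**What the plan says.** **Threshold and force.** Section 4.4.1 introduces its list as "Reasons subjects may be withdrawn from this research study", which is permissive. One entry is "Disease progression or a 50% increase in seizure frequency (compared to baseline"), naturally read as reaching 1.5 times baseline. Section 8.5, headed Stopping Rules, lists "Increased seizure frequency (more than 50% compared to base line"), which means exceeding 1.5 times baseline. Section 8.6.1 repeats that list. Neither 8.5 nor 8.6.1 attaches a specific action to it. Both say only that the principal investigator is informed and acts to keep the patient safe.

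**Counting period.** None of the three sections gives one. Eligibility in 4.1 is at least 2 "seizures per week (mean of total over 1 week"), and section 4.3 says: "Patients will be asked to keep a daily seizure diary (minimum of 1 week), before they come for their first evaluation at Mayo Clinic". Section 3.2 gives a per-week unit for relapse. Neither the eligibility week nor the relapse unit is tied to this rule.

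**Reporting.** Section 8.5: "Any adverse event should be reported to the coordinator within 24-48 hours by the patient". Section 8.6.1, in a parallel paragraph followed by the same four events: "Any serious adverse event should be reported to the coordinator within 24-48 hours by the patient". Section 3.2 separately sends any rise in seizure frequency, with no threshold, to the principal investigator or a designee "to determine if any action should be taken or if un-blinding is required".

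**The concern.** Seizure counts near the entry threshold are small whole numbers, so a rise of exactly 50% (2 to 3, 4 to 6, 6 to 9) is common. A patient at that point meets 4.4.1 but not 8.5 or 8.6.1. With no period stated, one member of staff could judge each week and another the average since the first infusion, and they would often disagree about the same diary.

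This is more than untidy wording. Section 8.5 offers the stopping rules as the safeguard that makes a five-week delay of treatment acceptable in the placebo group. Staff should be able to tell from the text when the safeguard is met, whether acting on it is required, and what the patient has been told to report. The rule also operates before the week-6 primary assessment, and section 7.1 does not say how a patient withdrawn for worsening is classified.

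**Working it through.** The documents give no figure for how often this rule would be met, so there is none to reproduce. The stated power (89% with 15 per group, 70% v 10%) does reproduce: full enumeration of the two-sided Fisher test gives 89.4%. This point does not affect it.

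**Inputs.** Entry threshold of 2 per week (4.1); baseline diary of at least one week (4.3); five weeks of blinded treatment (3.1). Assumptions, not in the documents: weekly counts are Poisson, independent between weeks, and the true rate is unchanged from baseline.

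**Rules.** With baseline b and weekly count X, version A (4.4.1) is X ≥ 1.5b, and version B (8.5, 8.6.1) is X > 1.5b.

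**1. Fixed baseline of 2, one week.** Poisson(2) probabilities for counts 0, 1, 2 and 3 are 0.1353, 0.2707, 0.2707 and 0.1804.
- A needs X ≥ 3: 1 − 0.6767 = 32.3%.
- B needs X ≥ 4: 1 − 0.8571 = 14.3%.
- Ratio 0.3233/0.1429 = 2.26.

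**2. Other fixed baselines, one week.**
- 4 per week: 21.5% v 11.1% (ratio 1.94).
- 6 per week: 15.3% v 8.4% (1.82).
- 10 per week: 8.4% v 4.9% (1.71).
- 3, 5 or 7 per week: identical, because 1.5b is not a whole number.

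**3. Clustering.** Negative binomial counts with mean 2 and variance 2.4, 4 and 10 give ratios of 2.04, 1.67 (31.3% v 18.8%) and 1.37 (26.7% v 19.5%).

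**4. Baseline observed in one week.** True rate 2, baseline week Y kept only if Y ≥ 2. The weights for Y = 2, 3, 4 are 0.456, 0.304 and 0.152; larger Y adds almost nothing.
- A: 0.456×0.3233 + 0.304×0.0527 + 0.152×0.0166 ≈ 16.6%.
- B: 0.456×0.1429 + 0.304×0.0527 + 0.152×0.0045 ≈ 8.2%.
- Ratio 2.03.

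**5. Effect of the period, same observed baseline.** For any of five weeks, take 1 − (1 − p)^5 within each baseline value and then average over baselines.
- A: 0.456×0.858 + 0.304×0.237 + 0.152×0.080 ≈ 48%.
- B: 0.456×0.537 + 0.304×0.237 + 0.152×0.022 ≈ 32%.
- At true rates of 3 and 10 per week, A v B is 54% v 47% and 44% v 40%.

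For the five-week mean at 2 per week, the total is Poisson(10) and A needs a total of at least 7.5Y. For Y = 2 that is 15 or more, probability 0.0835. For Y = 3 it is 23 or more, about 0.0003. So A is 0.456×0.0835 + 0.304×0.0003 ≈ 4%.

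At 2 per week, then, the choice of threshold moves the any-week figure from 48% to 32%, while the choice of period moves version A from 48% to 4%.

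**6. Reporting delay.** Section 6.14 schedules diary and adverse-event review at weeks 1 to 6, nominally a week apart. With the ±3 day window the longest gap between consecutive weekly contacts is 7 + 3 + 3 = 13 days.

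**The case against.** The strongest reply is that little turns on the wording. Withdrawal under 4.4.1 is discretionary, the same entry also allows disease progression, and the list includes safety issues generally. A patient at exactly 50% can be withdrawn or kept under either threshold. This stands. A reader might infer that stable patients will be removed by chance and that the 15 per arm will shrink. The documents do not support that: the probabilities count patients who meet a rule, nothing makes withdrawal automatic, and an early termination visit with diary review is planned where possible.

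It is also fair to say that a factor of two is close to the largest case. It needs a baseline at the entry threshold, a one-week window and little clustering, so it should not be read as applying to the whole trial.

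On reporting, a reader might infer that 8.6.1 frees the patient from reporting worsening seizures, because 8.1 does not list a seizure increase as serious. That goes too far. The four events after the 8.6.1 sentence include this one and can be read as covered by it. Section 8.1 has a catch-all for events that the sponsor-investigator judges to affect safety. Section 3.2 escalates any increase, provides 24-hour emergency contact details and sits alongside roughly weekly contacts. A patient who follows 8.5 also satisfies 8.6.1.

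What remains is that the sections differ on threshold and reporting scope, leave the force of the rule unclear and give no period. Section 3.2 is a staff escalation step with a third, threshold-free trigger. It does not settle what the patient must report or when the stopping rule is met.

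**Conclusion.** The inconsistency is real and should be corrected, because section 8.5 relies on these rules to justify delaying treatment. The threshold wording alone changes the one-week probability from 32% to 14% at a fixed baseline of 2 per week, or from 17% to 8% when the baseline is one observed week. Under strong clustering the ratio is about 1.4, and at fixed odd baselines the wording makes no difference. The absent counting period is the larger gap: 48% v 4% for the 4.4.1 version at 2 per week. All of these figures rest on Poisson counts (negative binomial for the clustering range), independent weeks and an unchanged true rate, none of which the documents supply.

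No loss of patients, power or blinding has been shown, and any reporting delay is limited by the contact schedule. Which threshold or period is clinically right is not a question this check can answer.

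**What to change.** Reconcile sections 3.2, 4.4.1, 8.5 and 8.6.1 so that all state:
- one threshold, explicit about whether equality counts;
- one period for counting on-study frequency, and the baseline it is compared with;
- whether action is mandatory or discretionary, and how the rule relates to the escalation in 3.2;
- one patient reporting duty that expressly covers a seizure increase.

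The sponsor chooses the clinical content.

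As a separate analysis point, add a sentence to 7.1: patients withdrawn for seizure worsening before week 6 stay in the primary Fisher comparison, in their randomised arm, as non-responders. Section 7.1 discusses dropout as a smaller number per group (20% of 15 is 3, leaving 12), which suggests that such patients would leave the denominator. Dropping them would remove failures because of their outcome. The small downside is that a stable patient withdrawn by chance is counted as a non-responder.

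The cost is wording in four protocol sections and one sentence in the statistical plan, with no change to sample size or visits.
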